5.3. Number of patients

Expected number of subjects is 200 patients. Subjects who initiate the multidisciplinary weight loss treatment during the study inclusion period, meet the inclusion and exclusion criteria, and agree to participate and sign the informed consent will be included in the study.

6. TREATMENT DESCRIPTION

The standardized multidisciplinary method under study is a weight loss program consisting of different stages. The initial stage (stage 1) is based on a protein diet, a type of ketogenic diet very low in calories. This stage is followed by a physiological adaptation stage (stage 2) in which all food groups are reintroduced progressively, and a maintenance phase (stage 3) with long-term monitoring of the patient's weight to ensure stability of the results obtained. This program contemplates other essential aspects in the management of obese patients, such as dietary education, physical activity and psychological support throughout the treatment.

80% of target weight loss			20% of target weight loss	Long-term maintenance of weight loss
Multidisciplinary team (dietary counselling / physical activity / psychological support)				
Stage 1 Active Stage		Stage 2 Dietary re-education		Stage 3 Maintenance
Phase 1	Phase 2	Phase 3	Gradual re-introduction of different foods	
VLCK diet ¹ (600-800 kcal/day)		LC diet ² (800-1500 kcal/day)		Maintenance diet (1500-2250 kcal/day)

The stage 1 protein diet is established through the intake of high biological value proteins and low-glycaemic vegetables, supplemented with micronutrients (potassium, sodium, calcium, magnesium, vitamins and trace elements) to avoid deficiencies. This stage consists of 3 phases (Phase 1, Phase 2a and Phase 2b), in which a protein preparation and then a second protein preparation are replaced progressively by protein-rich natural foods (meat/fish/eggs). During this period of ketogenic diet, the patient will be visited by the doctor every fortnight.

The ketogenic stage 1 of the method will be maintained for 2 months for those patients with an initial BMI of 30 to 35 kg/m² and for 3 months for those patients with initial BMI > 35 kg/m².

Stage 2 begins after the initial loss of most of the weight to be lost (ideally 80%), with the progressive introduction of different foods, while reducing protein preparations at the same time. In this way the weight loss indicated by the doctor is finally reached and the food balance is also achieved. This stage will be maintained for a period of 4 months in patients with an initial BMI of 30 to 35 kg/m² and for 6 months for those patients with initial BMI > 35 kg/m².

The last stage of the method begins at this moment, which involves the long-term maintenance of the lost weight, with the supervision and monitoring of specialized dietitians/nutritionists who advise patients in terms of consolidation of their new dietary habits, that is, the establishment of a balanced diet, which is the ultimate goal of the method.

The method must be implemented under strict medical supervision to ensure the efficacy and, above all, the safety of the program. In addition, the program is supported

by dietitians/nutritionists who help control the patient's progress (with continuous on-site and/or telephone follow-up over the 2 years of treatment) and a team of psychological counselling professionals and experts in physical activity.

7. STUDY PROCEDURES

7.1. Start of study

The investigating physician will be responsible for assessing the appropriateness of the treatment for each patient, regardless of their participation in this study.

Patients will be recruited consecutively as they go to the clinic and are prescribed treatment with the standardized multidisciplinary method. Before being included, the investigator must check the inclusion and exclusion criteria, and obtain their informed consent.

[figure not shown]
7.2. Follow-up period

The expected follow-up period for each patient will be 2 years from the time of inclusion, recording data during the weight loss and maintenance periods. The registry of patient data for this study will be made by the doctor and the dietitians/nutritionists who will regularly see the patient in the face-to-face visits at the Pronokal centre. For this, a specific form will be designed in which information about the variables to be studied will be collected.

Before starting treatment with the standardized multidisciplinary method and its inclusion in the study, the physician will have performed a first patient pre-inclusion visit (day -15) to request complementary tests (laboratory and ECG) and rule out the existence of contraindications to the ketogenic diet part of the weight loss program.

The study will begin with the baseline visit (day 0) in which the inclusion and exclusion criteria will be confirmed, the signing of informed consent will be obtained and the multidisciplinary treatment will be prescribed, followed by 6 control visits: 2 visits during the ketogenic stage (1-month after the start and at the end of ketosis), 2 visits during the physiological adaptation phase (at 4 or 5 months and at the end of stage 2) and 2 follow-up visits during the maintenance up to the 2-year completion. Regardless of the visits established in this protocol, the doctor will make as many visits as he/she deems necessary for good patient control.

On the other hand, dietitians/nutritionists, according to the methodology of the program, will carry out a face-to-face follow-up of the patient, which will be fortnightly during the ketogenic diet, monthly during the physiological adaptation of stage 2 and quarterly or semi-annual during the maintenance stage.

In the **pre-inclusion visit (day -15)**, the physician will perform a first clinical assessment of the patient. He/she will record the sociodemographic data, history of diabetes, comorbidities, pharmacological treatments. He/she will request complete laboratory tests and will perform an electrocardiogram to rule out contraindications and verify the inclusion/exclusion criteria. The said laboratory tests will include:

- Complete blood count and leukocyte formula
- Hydrocarbon metabolism: fasting glycemia, HbA1c, insulinemia
- Lipid profile: total cholesterol, LDL-C, HDL-C, triglycerides
- Transaminases: GOT, GPT, gammaGT
- Renal profile: creatinine, glomerular filtration, creatinine clearance, microalbuminuria
- Nitrogen balance: urea, uric acid
- Thyroid profile: TSH, T3, T4
- Ionogram: Na, K, Cl, Ca, Mg

In the **initial visit (day 0)**: In this visit, a physical examination will be performed and data related to weight (weight, BMI, waist circumference), as well as data on comorbidities associated with obesity (type of pathology, pharmacological treatment, complications in the last year) will be recorded. After checking the inclusion/exclusion criteria, the patient information sheet will be given and the informed consent will be obtained. During this visit, the patient's quality of life will be assessed (with the SF-12 quality of life questionnaire) and treatment will be prescribed according to the method (PronoKal® Method), which will begin with phase 1 of the active stage.

PRONOCOST study. Cost-effectiveness pharmacoeconomic study of a standardized multidisciplinary weight loss method (PronoKal® Method) to improve health condition of obese patients with associated comorbidities.

In the **follow-up visits - Recorded by the doctor**. In the regular check-ups throughout the course of treatment, the physician will record: any discomfort or side effect related to weight loss treatment and whether there has been any change in the comorbidities associated with obesity (laboratory results, medication, complications, etc.). At the end of each stage the doctor will assess the patient's quality of life through a questionnaire.

In the **follow-up visits - Recorded by dietitians/nutritionists**. During the interviews that the dietitians/nutritionists will have with the patients, and parallel to the doctor's records, the following details will be recorded:

- Clinical data: anthropometric data and blood pressure
- Medication changes
- Onset of complications (e.g., hypertensive crisis, ...)
- Hospital admissions
- Work absenteeism: number of days and cause....

In case of early withdrawal from the study, the doctor will write the dropout date and the reason, in study completion form.

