8.1. Source of information

The information for this study will be obtained from the patient's medical records and the interview that the physician and dietitians/nutritionists carry out with the patient. All information will be recorded on the forms designed for this purpose (Annex 3) and subsequently submitted to the coordinating center, prior express authorization of the patient by signing the Informed Consent, for its statistical analysis.

The corresponding data will be saved in a file owned by PronoKal Group®, who will manage the information according to Organic Law 15/1999 relative to Protection of Personal Data.

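### Absenteeism and hospital admissions are gathered at interviews whose spacing widens from 2 weeks to 3 or 6 months with no common recall period, so imperfect recall can distort the course within follow-up and shift the before-after comparison in either direction.

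*Combined protocol and SAP*

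**What the plan says.** Section 7.2 sets the dietitian contacts as "fortnightly during the ketogenic diet, monthly during the physiological adaptation of stage 2 and quarterly or semi-annual during the maintenance stage". It does not say which patients are seen quarterly and which semi-annually in maintenance. It then states: "During the interviews that the dietitians/nutritionists will have with the patients, and parallel to the doctor's records, the following details will be recorded". The list that follows covers anthropometry and blood pressure, medication changes, complications, hospital admissions and "Work absenteeism: number of days and cause".

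The doctor's follow-up list in the same section covers side effects and "whether there has been any change in the comorbidities associated with obesity (laboratory results, medication, complications, etc". It names neither admissions nor absenteeism. Six doctor control visits are scheduled, of which "2 follow-up visits during the maintenance up to the 2-year completion"; the doctor may add others.

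Section 8.1 says that the data are "obtained from the patient's medical records and the interview that the physician and dietitians/nutritionists carry out with the patient". Section 6 mentions "continuous on-site and/or telephone follow-up over the 2 years of treatment", but section 7.2 ties recording to face-to-face visits and does not name the telephone as a collection point.

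Section 9.1 makes resource consumption (including admissions), drug changes and absenteeism the primary endpoints. Section 10.2 compares healthcare expenses and absenteeism in the 6 months before treatment, taken from the doctor's records, with data from the follow-up visits over 2 years.

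**The concern.** The contact schedule follows the needs of the weight-loss programme. An endpoint that counts days off work, or minor use of care, needs the same chance of being recorded in every month. Here a short absence in stage 1 is asked about within about 2 weeks, while the same absence in maintenance may be asked about up to 6 months later. Section 10.2 also costs items that are easily forgotten, such as hours lost to medical visits, antibiotic courses and general practitioner visits.

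Two things are at stake. A falling rate across stages could reflect recall and not health, and patients on quarterly and semi-annual contact would not be comparable. The planned before-after comparison would also set a single 6-month look-back against a mixture of 2-week, 1-month and 3- or 6-month look-backs, from a different source.

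**Working it through.** The documents give no figure for recall or completeness, so there is no stated number to reproduce. The contact schedule can be computed from the text. The size of the bias needs an assumption, which is varied below.

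**Time in each stage (section 6; 24 months in total)**

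- BMI 30-35: stage 1 is 2 months and stage 2 is 4 months, so maintenance is 24 - 6 = 18 months (18/24 = 75%).
- BMI > 35: stage 1 is 3 months and stage 2 is 6 months, so maintenance is 24 - 9 = 15 months (15/24 = 62.5%).

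**Dietitian contacts (section 7.2)**

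- BMI 30-35: about 4 in stage 1, 4 in stage 2, and 18/6 = 3 (semi-annual) to 18/3 = 6 (quarterly) in maintenance.
- BMI > 35: about 6 in stage 1, 6 in stage 2, and 15/6 = 2.5, so 2 or 3 (semi-annual), to 15/3 = 5 (quarterly) in maintenance.
- The interval widens from 2 to 26 weeks, about 13-fold.

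**Recall model (assumption)**

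The true event rate is constant, and an event not yet reported is forgotten at a fixed proportion d per month. With λ = -ln(1 - d), the share captured by an interview looking back T months is c(T) = (1 - exp(-λT))/(λT).

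Worked case, d = 5%: λ = 0.0513.

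- c(2 weeks) = 0.988 and c(1 month) = 0.975.
- c(3 months) = (1 - 0.95³)/(3 × 0.0513) = 0.927.
- c(6 months) = (1 - 0.95⁶)/(6 × 0.0513) = 0.861.

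*Within follow-up.* Stage 1 to semi-annual maintenance: 0.861/0.988 - 1 = -12.9%. Stage 1 to quarterly maintenance: 0.927/0.988 - 1 = -6.2%. During maintenance, semi-annual patients appear 1 - 0.861/0.927 = 7% lower than quarterly patients.

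*Against baseline.* For BMI 30-35 with semi-annual contact, the 2-year average capture is (2 × 0.988 + 4 × 0.975 + 18 × 0.861)/24 = 0.890. Against a complete baseline this is -11.0%. Against a baseline with one 6-month look-back and the same loss, it is 0.890/0.861 - 1 = +3.4%.

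The ranges in the last two columns cover both BMI groups and both maintenance schedules.

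| Monthly loss (assumed) | Stage 1 to quarterly | Stage 1 to semi-annual | 2-year average vs complete baseline | 2-year average vs baseline with 6-month recall |
|---|---|---|---|---|
| 0% | 0% | 0% | 0% | 0% |
| 2% | -2.5% | -5.4% | -2.2% to -4.6% | +1.3% to +3.9% |
| 5% | -6.2% | -12.9% | -5.3% to -11.0% | +3.4% to +10.0% |
| 10% | -12.2% | -24.1% | -10.5% to -20.5% | +7.3% to +20.8% |
| 20% | -23.3% | -42.0% | -20.2% to -35.8% | +16.5% to +44.9% |

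**Cross-check with flat capture rates (assumed)**

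Suppose 95% capture at up to 1 month and 70-85% at 6 months.

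- Fall within follow-up: 1 - 0.85/0.95 = 10.5% to 1 - 0.70/0.95 = 26.3%.
- BMI 30-35, against a baseline with the same 6-month capture: (6 × 0.95 + 18 × 0.70)/24 = 0.7625, and 0.7625/0.70 = 1.09. With 0.85 in place of 0.70, 0.875/0.85 = 1.03. Follow-up looks 3-9% higher.
- BMI > 35: (9 × 0.95 + 15 × 0.70)/24 = 0.794, and 0.794/0.70 = 1.13. With 0.85, 0.8875/0.85 = 1.04. Follow-up looks 4-13% higher.

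Both models agree: downward within follow-up, and upward against a baseline with equal 6-month recall.

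**Effect of a fixed look-back**

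At d = 5%, a 3-month form throughout follow-up removes the artefact across stages. It still leaves 0.927/0.861 - 1 = about +8% against a 6-month-recall baseline, or 0.927 - 1 = about -7% against a complete one. A 6-month form in both periods gives 0.861/0.861 - 1 = 0%, and the ratio is 1 at any loss rate.

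**The case against.** A reader might infer that thinning contact manufactures the very reduction the study hopes to show. The documents do not support that. Section 10.2 does not plan a trend within follow-up for expenses and absenteeism; it compares follow-up with the 6 months before treatment. If that baseline suffers the same 6-month recall, the denser early contacts raise follow-up counts and the bias works against the programme. It favours the programme only if the doctor's records are more complete than the follow-up interviews, and the documents do not say whether they are.

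A reader might also infer that all primary variables depend on dietitian interviews. They do not. The doctor records medication and complications in parallel, extra doctor visits are allowed, and medical records are a named source. Acute visits and antibiotic courses are absent from the dietitian list and appear only as cost items in section 10.2. These points narrow the concern mainly to absenteeism and minor outside care. Admissions share the schedule, but no recall loss has been shown for them.

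Wider spacing alone loses nothing if each interview covers all the time since the last one and recall is perfect. That is correct, and it is the zero row of the table. Nothing in the available text secures it. The recording forms (Annex 3) and a figure in section 7.1 are not in that text and could state a look-back or a schedule, so the absence of a recall period can be asserted only for what was available.

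What stands is that ascertainment of absenteeism, a primary endpoint, varies by stage and between patients, and is not aligned with the baseline.

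**Conclusion.** The concern holds as a problem of unequal ascertainment, not as a bias of known direction. The widening of the interval, and the listing of follow-up admissions and absenteeism only under the dietitian interviews, are matters of text. Between 62.5% and 75% of follow-up lies in the sparsely observed stage.

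The size is conditional on the assumed recall loss, a constant true rate and equal forgetting before and after the start of treatment. At 5% per month the artefact is a 6-13% fall within follow-up. The error in the 2-year average against baseline ranges from 11% too low to 10% too high, depending on how complete the baseline is. The plan as written gives no way to tell which applies, so an observed change of about that size could not be attributed to the programme with confidence.

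**What to change.** In sections 7.2 and 10.2, specify one standard form for absenteeism, admissions, complications and outside visits, completed for all patients with a fixed 6-month look-back at day 0 and at months 6, 12, 18 and 24. Use the same items and the same source at day 0 as in follow-up. If medical records supplement the interview, extract them for the same windows in both periods. Name the telephone as a permitted collection route where no visit falls due.

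In section 10.2, base the primary before-after comparison on these matched windows. Keep the fortnightly and monthly entries for safety and for a sensitivity analysis. Reconcile the day 0 list in section 7.2, which asks for complications over the last year and names neither absenteeism nor admissions, with the 6-month baseline that section 10.2 needs.

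The cost is protocol wording, one form and a few calls. Month 6 falls within stage 2 or at its end for every patient, so at most three time points (months 12, 18 and 24) could need a call, and fewer where a visit coincides. The drawback is that recall in the active stage becomes longer than it could be. That is accepted so that any loss is the same in every window. The fix does not make recall complete; it removes the difference in look-back between the periods compared, provided that forgetting is similar before and after.

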9.2. Secondary endpoints

- Body weight and waist circumference
- Changes in clinical parameters: glycaemic profile, lipid profile, blood pressure
- Score in the SF-12 quality of life questionnaire
- Onset of side effects
- Onset of serious adverse reactions during the protein diet's follow-up.

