10. STATISTIC ANALYSIS

10.1. Descriptive statistics

Descriptive statistics will be made of all the variables collected in the Case Report Form, building frequency tables for the nominal-type variables and measurements of central tendency and dispersion for continuous variables. The 95% confidence intervals (95% CI) will be estimated for the latter.

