11. RECORDING ADVERSE REACTIONS

During the entire follow-up period, the physician should report any suspicion of a serious adverse reaction observed in the patient under treatment by completing a Serious Adverse Reaction Report form, forwarding it to the coordinating center (Annex 5).

PRONOCOST study. Cost-effectiveness pharmacoeconomic study of a standardized multidisciplinary weight loss method (PronoKal® Method) to improve health condition of obese patients with associated comorbidities.

SERIOUS ADVERSE REACTION: refers to any adverse reaction that can be classified in one or more of the following categories:

- Fatal
- Life-threatening
- Causes persistent or significant disability
- Causes hospitalization or prolongs hospital stay

Congenital anomalies/birth defects and serious adverse clinical consequences associated with use under conditions other than those set out in the Summary of Product Characteristics (SmPC), overdose or abuse are also included.

Medical judgment should be implemented when deciding whether an event or reaction is serious in other situations. Major adverse reactions or events that do not pose an immediate danger to life or cause death or hospitalization but which may endanger the patient should be considered serious.

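### The safety analysis counts only side effects and suspected reactions, one safety endpoint's time window conflicts with the rest of the plan, and event proportions get no confidence interval, so tolerability can look better and more certain than the data allow

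*Combined protocol and SAP*

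**What the plan says.** Sections 1.8 and 3.2 list tolerability and safety among the secondary objectives. The rules that bear on it are spread over five places.

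- **Collection (7.2).** At follow-up the doctor records "any discomfort or side effect related to weight loss treatment" and, with no condition on cause, "whether there has been any change in the comorbidities associated with obesity (laboratory results, medication, complications, etc". The dietitians separately record "Onset of complications (e.g., hypertensive crisis" and "Hospital admissions", also with no condition on cause. For early withdrawal, the date and reason go on the completion form.
- **Endpoints (9.2).** There are two safety endpoints: "Onset of side effects", with no time window, and "Onset of serious adverse reactions during the protein diet's follow-up".
- **Safety analysis (end of 10.2).** Patient-reported side effects and adverse reactions are summarised descriptively over the whole study. Admissions and complications appear in 10.2 as components of healthcare cost.
- **General description (10.1).** Every variable on the case report form is to be described, nominal variables by frequency tables and continuous ones by location and spread. Intervals are then promised for the continuous variables: "The 95% confidence intervals (95% CI) will be estimated for the latter".
- **Serious reactions (11).** "During the entire follow-up period, the physician should report any suspicion of a serious adverse reaction".

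**The concern.** Three features act on the same objective.

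First, the safety analysis is built on terms that presuppose a link to treatment. No safety table is planned that counts events regardless of cause. The doctors who record relatedness also deliver the programme, sections 4 and 5 provide no comparator, and the supplied text describes no method for judging causality. Less filtered information is collected, but it is not brought into the safety analysis. An admission could count in the cost results and be absent from the safety results of the same report.

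Second, the serious-reaction endpoint carries a time window that the analysis and reporting sections do not share. If this is not settled beforehand, the window could be chosen after the events are known.

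Third, adverse event counts will be small, and that is where a bare percentage misleads most. With no interval, zero or two events in 200 patients can be taken as evidence of safety that the sample cannot provide.

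**Working it through.** The plan states no expected event rate, precision target or sample-size derivation, so there is no figure of its own to reproduce. Section 5.3 gives 200 only as an expected number.

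**1. How much follow-up the 9.2 window covers.** Inputs: follow-up of 24 months (7.2); stage 1 of 2 or 3 months and stage 2 of 4 or 6 months, depending on baseline BMI (section 6).

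| Reading of the protein diet | Months | Share of 24 months |
|---|---|---|
| Stage 1 only | 2 or 3 | 2/24 = 8.3%; 3/24 = 12.5% |
| Stages 1 and 2 | 2+4 = 6 or 3+6 = 9 | 6/24 = 25%; 9/24 = 37.5% |
| Sections 10.2 and 11 | 24 | 100% |

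Under either of the first two readings, an analyst who follows 9.2 leaves out most of the period that 10.2 and 11 include.

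**2. What a small count allows.** Exact (Clopper-Pearson) two-sided 95% limits. For zero events the upper limit is 1 − 0.025^(1/n). For x events it is the 0.975 quantile of a beta distribution with parameters x+1 and n−x. The plan gives no dropout figure, so evaluable numbers below 200 are assumptions.

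| n | Upper limit, 0 events | Upper limit, 2 events |
|---|---|---|
| 200 (section 5.3) | 1.83% | 3.57% |
| 160 (assumed) | 2.28% | 4.44% |
| 140 (assumed) | 2.60% | 5.07% |
| 100 (assumed) | 3.62% | 7.04% |

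The probability of seeing no event at all is (1 − p)^n. With n = 200, a true risk of 1% gives 0.99^200 = 0.134, and a true risk of 0.5% gives 0.995^200 = 0.367.

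**3. What counting only related events can do.** Related events are a subset of all events, so their count can be equal or lower but never higher. The documents do not give the size of the gap. As an illustration, assume that 20 of 200 patients have an event of any cause and that 25% to 75% of these are judged related.

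- All causes: 20/200 = 10.0% (exact 95% interval 6.22% to 15.02%).
- 75% judged related: 15/200 = 7.5% (4.26% to 12.07%).
- 25% judged related: 5/200 = 2.5% (0.82% to 5.74%).

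In the last case the interval around the related-only rate excludes the all-cause rate of 10%. Adding intervals therefore does not remove the need for the all-cause tables; the two changes address different problems.

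**The case against.** The strongest reply is that the plan is broader than 7.2 and 9.2 suggest on their own. Several tempting inferences fail against it.

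- *Every event must pass a causality verdict from the programme's doctor.* The text does not say so. Section 10.2 speaks of what patients report, and section 11 asks for mere suspicion. What stands is that the terms used still imply a link to treatment.
- *Admissions and complications serve only as cost data.* Section 10.1 promises a description of every case report form variable, so they would be tabulated if they are on the form. What is missing is narrower: they are not in the safety analysis, and no breakdown by stage or by suspected relation is planned.
- *The 9.2 wording means serious reactions will be lost.* Section 11 collects them over all of follow-up, section 10.2 analyses reactions over the whole study, and the other safety endpoint has no window. This is a contradiction to resolve, not a demonstrated loss of events.
- *The window is simply 8-13% of follow-up.* That is one reading. Section 6 uses the term for stage 1, but protein preparations continue, in decreasing amounts, in stage 2, and section 2 describes the whole method as protein-based. On that widest reading the conflict disappears, which is itself a reason to state the period.

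It is also fair to say that a reader can compute an exact interval from any count and denominator, that the objective is secondary and descriptive, and that the forms in Annexes 3 and 5 are not in the supplied text and may hold more fields. Extra fields would not by themselves change the analysis described in 10.2.

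**Conclusion.** The point holds, as a weakness in how safety will be analysed and presented. The safety analysis rests on side effects and suspected reactions in a single-arm study. The endpoint window in 9.2 disagrees with 10.2 and 11, covering 8-13% or 25-38% of follow-up on its two narrower readings. No interval is planned for any event proportion, although with 200 patients zero events leaves a true rate up to 1.83% open and two events up to 3.57%. These limits assume that all 200 patients are evaluable; with fewer they are wider.

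A reader might conclude that tolerability will look better than it is. The documents support only that it can: the share of events judged unrelated is unknown, and it may prove small. The primary cost-effectiveness objective is not affected. The changes are worth making because they are cheap and rely almost entirely on data already planned.

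**What to change.** 1. **Section 9.2.** Reconcile the window of the serious-reaction endpoint with 10.2 and 11, so that serious reactions are analysed over the entire follow-up.
2. **Section 10.2.** Add to the safety tables all recorded hospital admissions and complications, and all withdrawals with their reason, including death, regardless of cause and by treatment stage. Show separately those reported as suspected reactions. Name death explicitly, because 7.2 does not list it as an item; it would otherwise surface only as a reason for withdrawal or as a fatal reaction under section 11.
3. **Section 10.1.** Give exact 95% confidence intervals for proportions, including adverse event and withdrawal rates, with the denominator stated.

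The cost is some wording and a few extra tables, and reported event rates may be higher. One limit remains: non-serious events that the doctor does not consider related, and that are neither complications nor changes in a comorbidity, may still go unrecorded under 7.2. The report should say so.

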7.3. Duration of study

For each patient initiating treatment, a minimum follow-up period of 2 years will be observed.

8. SOURCE OF INFORMATION AND DATA MANAGEMENT.

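### The plan promises two years of follow-up for every patient who starts, but sets out no way to collect cost, drug or absence data once a patient stops the method

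*Combined protocol and SAP*

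**What the plan says.** Section 7.3 sets the commitment: "For each patient initiating treatment, a minimum follow-up period of 2 years will be observed". It applies to all who start, whether or not they continue.

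Section 7.2 describes how data are gathered. The registry is filled in by the doctor and the dietitians "who will regularly see the patient in the face-to-face visits at the Pronokal centre", and the recording window is tied to the stages of the method: "The expected follow-up period for each patient will be 2 years from the time of inclusion, recording data during the weight loss and maintenance periods". Entries by the doctor are made during treatment ("In the regular check-ups throughout the course of treatment, the physician will record"). The dietitians note medication changes, complications, admissions and absenteeism at their own interviews. In the last stage there are "2 follow-up visits during the maintenance up to the 2-year completion" with the doctor, plus dietitian visits every three or six months.

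For a patient who leaves early, section 7.2 says: "In case of early withdrawal from the study, the doctor will write the dropout date and the reason, in study completion form".

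Two other places bear on the point. Section 8.1 names records and interviews as sources: "The information for this study will be obtained from the patient's medical records and the interview that the physician and dietitians/nutritionists carry out with the" (last word omitted). Section 6 describes dietitian support "with continuous on-site and/or telephone follow-up over the 2 years of treatment".

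Section 10.2 compares expenditure and absenteeism in the six months before treatment with what is recorded at follow-up visits over the two years. Section 10 defines no analysis population and no handling of missing or censored cost data. Section 5.3 gives an expected 200 patients and no dropout rate.

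**The concern.** The visits that deliver the method are also the visits that supply the study data. A patient who gives up the programme loses the scheduled contacts at which drugs, complications, admissions and days off work would be asked about. The plan provides no other contact, and it does not say whether such a patient is still in the study.

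People who stop a diet programme plausibly include those who lost little weight, regained it or tolerated the diet poorly. Their drug use and costs may drift back towards the starting level. The objective in section 3.1 concerns patients treated with the method, not only those still attending at two years. If the comparison rests on attendees, the estimated saving probably comes out too large. This has to be settled before follow-up ends, because an analysis rule cannot replace data that were never collected.

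**Working it through.** The plan states no figure that can be reproduced here, so the check has two parts.

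**Is there a route to the data after a patient stops?**

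| Possible route | Where | Set up for patients who have stopped? |
|---|---|---|
| Doctor's check-ups | 7.2 | No; made during treatment |
| Dietitian interviews | 7.2 | No; face-to-face, following the programme's schedule |
| Study completion form | 7.2 | Date and reason are the only items named |
| Medical records | 8.1 | Named as a source; no review after stopping is scheduled, and whose records are meant is not said |
| Telephone contact | 6 | Programme support during treatment; not described as study data |
| Two-year minimum | 7.3 | A commitment without a procedure |

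The commitment covers these patients, but no procedure carries it out.

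The exposed period is long. By the stage lengths in section 6, maintenance takes 24 − 2 − 4 = 18 months (75% of follow-up) for an initial BMI of 30 to 35, and 24 − 3 − 6 = 15 months (62.5%) above 35. With dietitian visits up to six months apart in that stage, up to about six months before a dropout could also go unrecorded if the last interval is not asked about.

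**How large could the effect be?**

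All inputs below are assumptions except the 24 months and the 200 patients:
- expenditure falls by 30% while a patient attends;
- it returns fully to baseline on stopping;
- a proportion D stops, evenly spread over the 24 months;
- nothing is recorded after stopping.

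On average a stopper misses half the period, so the share of planned patient-months lost is D/2. The planned total is 200 × 24 = 4,800.

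The recorded data show a 30% fall. The true mean fall over two years among all starters is 30% × (1 − D/2), and the overstatement is 1/(1 − D/2).

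| D | Patient-months lost | True two-year fall | Overstatement |
|---|---|---|---|
| 20% | 10% (480) | 27% | 1.11 |
| 30% | 15% (720) | 25.5% | 1.18 |
| 40% | 20% (960) | 24% | 1.25 |
| 50% | 25% (1,200) | 22.5% | 1.33 |

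The ratio does not depend on the 30%. If stoppers keep half the benefit (again an assumption), the factor becomes 1/(1 − D/4), which is 1.05, 1.08, 1.11 and 1.14.

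For a cross-section at month 24 the factor would be 1/(1 − D): 1.25, 1.43, 1.67 and 2.0. That is not the comparison planned in section 10.2, which covers the whole follow-up period.

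**The case against.** A reader might infer that data come solely from face-to-face visits and that patients who stop will contribute nothing afterwards. The documents do not support that.

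- Section 8.1 also names medical records and does not restrict interviews to face-to-face contact. Section 6 mentions telephone follow-up.
- The sentence on date and reason concerns leaving the study. Nothing says that stopping the method ends study follow-up, and section 7.3 read literally says the opposite.
- The data forms (Annex 3) are not in the text available, so the completion form may ask for more than section 7.2 lists.

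These points stand, and they limit the claim to an unspecified procedure. They do not close the gap: no record review or telephone interview is scheduled after stopping, and hours of absence depend largely on asking the patient.

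A reader might also take the bias in the method's favour as established, or quote an overstatement of up to 2.0 fold. The direction is likely but not shown, since the documents give neither the rate of nor the reasons for dropout, and some patients may leave for unrelated reasons or after reaching their target. The larger factor belongs to a month-24 cross-section, and full return to baseline is the extreme case.

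**Conclusion.** The concern holds as a gap in procedure. The plan ties the primary outcomes to programme visits, does not distinguish stopping the method from leaving the study, and does not say how the two-year minimum will be met for patients who stop. Followed as written, the two-year comparison would rest mainly on attendees and would probably overstate savings.

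The illustrative size is 1.11 to 1.33 fold for 20 to 50% dropout under full return to baseline, and smaller if part of the benefit persists. Both the dropout range and the return to baseline are assumptions. The gap in collection does not depend on them. Closing it is a cheap improvement.

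**What to change.** In section 7.2, define two separate events: the patient has stopped the method, and the patient has withdrawn consent to follow-up. For patients who have stopped but not withdrawn consent:

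1. At the last contact, where one occurs, record medication, complications, admissions, health-care visits and absence since the previous visit. Health-care visits are included because section 10.2 costs them.
2. At each remaining scheduled visit time to month 24, collect the same items by telephone, supplemented by medical records, using the dietitians already in the programme.
3. Record the date of stopping the method separately from the date of last data.
4. State in section 10.2 that these patients are included in the two-year primary comparison.

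The cost is some protocol wording, added form fields and a few calls per patient who stops. The consent wording must cover those calls, which cannot be checked from the text available. After stopping, weight and laboratory values will be self-reported or missing. The reported saving may also look smaller.
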